1.3 Schedule of Activities

| Visit | Screening | Vis Da | it 1/ y 1 | | it 2/ ek 6 | Safety Follow-up 1 ^j | Safety Follow-up 2 (EOS) ^j | Early Termination (ET) k,l |
|--|------------------------|---------------------------------|------------------------------------|---------------------------------|------------------------------------|------------------------------------|---|--------------------------------|
| Window | Day -30 to Day 1 | ± 0 | days | Week 6 t | o Week 8 | 1-3 Days After Visit 2 | 28 (± 3) Days After Visit 2 | <7 days from ET Decision |
| Timing of Activity(ies) | | Prior to ¹²⁴ I-AT-01 | ¹²⁴ I-AT-01 and Scan | Prior to ¹²⁴ I-AT-01 | ¹²⁴ I-AT-01 and Scan | | | |
| Assessment/Procedures | | | | | | | | |
| Informed Consent a | X | | | | | | | |
| Medical history and Demographics | X | | | | | | | |
| Inclusion and Exclusion criteria | X | | | | | | | |
| Concomitant Medications | X | X | X | X | X | X | X | X |
| Oral Potassium Iodide (KI) ^b | | X | | X | | | | |
| ¹²⁴ I-AT-01 Administration ^c | | | X | | X | | | |
| Biomarker and Safety Assessments | | | | | | | | |
| Vital Signs (HR and BP) d | | X | X | X | X | | | |
| Body Weight | | X | | X | | | | |
| Height | | X | | | | | | |
| Pregnancy Test (WOCBP) e,f | X | | | X | | | | |
| PET/CT Scan | | | X | | X | | | |
| Adverse events g | X | X | X | X | X | X | X | X |
| Laboratory h,i | X | | | X | | X | | |
| Biomarkers h,i | X | | | X | | | | |
| Urine UACR (AL subjects only) i | X | | | X | | | | |
| Serum ADA i | X | | | X | | | X | X |

Abbreviations: ADA = anti-drug antibodies; AL = amyloid light chain amyloidosis; BP = blood pressure; CBC = complete blood count; EOS = end of study; ET = early termination; HR = heart rate; NT-proBNP = N-terminal prohormone of brain natriuretic peptide; UACR = urine albumin-to-creatinine ratio; WOCBP = women of childbearing potential.

- a. Informed consent, as described in Section 10.1.3.
- b. KI is self-administered by the subject daily for 3 days, beginning >30 minutes and <24 hr prior to dosing, as described in Section 4.1.2.
- c. ¹²⁴I-AT-01 will be administered by IV infusion over 2-5 minutes (protocol Version 1.1) or slow IV bolus at 1 mL/5 seconds (protocol Version 2.0), as described in Section 4.1.3. For all subjects, ¹²⁴I-AT-01 will be administered by the same route (IV infusion over 2-5 minutes or slow IV bolus at 1 mL/5 seconds) at the Week 6 visit as on the Day 1 visit.

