- d. Subjects must remain semi-recumbent for at least 5 minutes prior to blood pressure measurements. Blood pressure and heart rate will be measured within an hour prior to dosing and 5-10 minutes after administration of ¹²⁴I-AT-01.
- e. Serum pregnancy test, as indicated in Section 10.2, will be obtained in all women of childbearing potential.
- f. Serum pregnancy and all other laboratory samples must be drawn within 7 days prior to administration of ¹²⁴I-AT-01 in all WOCBP. The results of the pregnancy test must be available and be negative prior to ¹²⁴I-AT-01 administration in all WOCBP.
- g. Adverse events will be monitored from Screening through the EOS Visit. For Safety Follow-up 1 and 2, adverse events and concomitant medications can be obtained by phone call.
- h. Clinical laboratory tests and biomarker analysis, as described in Section 10.2. Baseline sample will be collected within 30 days prior to the first administration of ¹²⁴I-AT-01; second sample within 7 days prior to the second administration of ¹²⁴I-AT-01; third sample at Safety Follow-up 1 after the second administration of ¹²⁴I-AT-01.
- i. Urine and blood may be collected locally by visiting nurse/phlebotomist. An additional serum ADA sample will be obtained at Screening for subjects who provided consent for the extra ADA sample.
- j. Safety follow-ups for concomitant medications and adverse events will be done via telephone call for all subjects. Both Safety Follow-up 1 and Safety Follow-up 2 activities will be conducted for subjects who discontinue for IRRs at either the first or second administration of ¹²⁴I-AT-01.
- k. Blood draw for ADA should be obtained if ET is ≥4 weeks after first administration of ¹²⁴I-AT-01.
- l. Early Termination activities do not apply to subjects discontinued for IRRs. Please follow Safety Follow-up 1 and Safety Follow-up 2 activities for subjects experiencing IRR with either the first or second administration of ¹²⁴I-AT-01.

- 15 -

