4.2.3 Choice of Duration of Treatment and Follow-up

 124 I-AT-01 is eliminated by radioactive decay (half-life ~ 4.2 days), cell-mediated protein clearance, and catabolism. Ten radioactive half-lives will assure complete clearance of radioactivity after the first PET/CT imaging visit and before the second PET/CT imaging visit. Ten half-lives is ~ 6 weeks. Thus, the two doses of 124 I-AT-01 will be separated by at least 6 weeks. A final safety follow-up 28 days after the second dose of 124 I-AT-01 represents more than five half-lives, a routinely recommended post-treatment safety assessment period (CIOMS 2005).

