9.5.4 Safety Analysis

Safety will be assessed through reported adverse events (graded using NCI CTCAE version 5) and changes in laboratory parameters.

Adverse Events

All adverse events occurring during the study will be recorded and classified based on Medical Dictionary for Regulatory Activities (MedDRA) terminology. Only treatment-emergent adverse events (TEAEs), which are adverse events that occur after the start of study drug, will be summarized.

The number and percentage of subjects experiencing TEAEs and SAEs will be tabulated for the safety population by system organ class (SOC) and preferred term (PT). TEAEs and SAEs will be tabulated by severity and relationship to study medication. Each subject will be counted only once within a SOC or a PT by using the AE with the highest severity or greatest relationship, respectively, within each category.

TEAEs or SAEs leading to early discontinuation will be summarized as described above. Treatment-emergent adverse events starting on the day of dosing at each dosing visit will be summarized by SOC and PT to evaluate potential infusion-related reactions.

Listings for all reported adverse events, including SAEs, will be provided. In addition, separate listing for SAEs, AEs leading to premature withdrawal from the study, and all deaths will be generated.

Vital signs will include blood pressure (mmHg) and heart rate (beats per minute). Vital signs will be summarized at Baseline and for each study visit when vital signs were obtained. Changes from Baseline in vital sign measurements will also be summarized. Baseline is defined as the last vital signs obtained prior to the initiation of study drug.

Clinical Laboratory Analyses

Baseline for clinical chemistry parameters is defined as the most recent laboratory measurement obtained prior to the initiation of study drug. Clinical laboratory parameters from the tests itemized in Section 10.2, will be summarized as both absolute value and change from Baseline for each visit per the SoA (Section 1.3).

Laboratory parameters with quantitative abnormalities will be listed as 'flagged' based on the Sponsor's internal guidelines. Flagged laboratory parameters will be presented by incidence and frequency.

Clinical safety laboratory tests performed during the study will be analyzed by a central clinical laboratory.

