4 GENERAL ANALYSIS AND REPORTING CONVENTIONS

The following general analysis and reporting conventions will be used:

- Categorical variables will be summarized using counts (n) and percentages (%) and will be presented in the form n (%). If a count is 0, no percentage will be shown. To ensure completeness, summaries for categorical variables will include all categories, even if no subjects had a response in a particular category. Denominators will include subjects with non-missing data, unless otherwise specified. The number of subjects with missing data for categorical variables will be summarized without a percentage.
- Continuous variables will be summarized using mean, standard deviation (SD), minimum, maximum, median, and number of subjects. The mean, median, and confidence intervals (CI) will be rounded and reported to 1 more level of precision than the original observations, and the SD will be rounded and reported to 2 more levels of precision than the original observations. The minimum and maximum will be the same precision as the original data.
- Following SAS default rules, the median will be reported as the rounded average of the two middle numbers if the dataset contains even numbers.
- P-values, if any are provided, will be rounded and reported to 3 decimal places if greater than 0.001. If the rounded p-value is less than 0.001, '<0.001' will be reported. If the rounded p-value is >0.999, '>0.999' will be reported.
- Unless otherwise specified, the baseline value for all measures is the last non-missing value prior to the first dose, obtained on or before the date of the first dose of study drug. For measurements that occur on the date of the first dose of study drug with time collected, the measurement will be considered the baseline value if the measurement time is prior to the time of the first dose.
- No preliminary rounding will be performed; rounding will only occur after analysis. To round, consider digit to right of last significant digit: if < 5 then round down, if ≥ 5 then round up.
- All listings will be sorted in order of subject, parameter (when applicable), and time of assessment (e.g., visit, time, and/or event).
- Dates in listings will be displayed as yyyy-mm-dd (e.g., 2021-10-14).
- Age (in years) will be calculated as [(date of informed consent date of birth)] /365.25 and will be reported as the integer part of the derived age, with no rounding, in the analysis datasets, tables, and listings.

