9.1 Overview of Safety Analysis Methods

The safety analyses will be performed for the Safety Set and will include treatment-emergent adverse events (TEAEs), serious adverse events (SAEs), vital signs, biomarkers, and concomitant medications. Tabular summaries of descriptive statistics will be presented for all subjects included in the Safety Set.

For all safety endpoints, baseline will b

e the last non-missing value before administration of ¹²⁴I-AT-01.

Safety data will not be imputed, except for partial and missing dates, which will be imputed only for defining TEAEs and concomitant medications. Imputed dates will not be presented in data listings.

Partial dates will be imputed for the purposes of defining TEAEs as follows:

- For a missing start day where the month and year are present, the start day will be set to the first day of the month, unless 1) the first day of the month is before the most-recent date of administration of ¹²⁴I-AT-01 and the month and year are the same as the month and year of the most-recent date of administration of ¹²⁴I-AT-01, and 2) the end date is on or after the most-recent date of administration of ¹²⁴I-AT-01or the end date is completely missing, in which case the start day will be set to the most-recent date of administration of ¹²⁴I-AT-01.
- For a missing start day and month where the year is present, the start day and month will be set to January 1st, unless 1) January 1st is before the most-recent date of administration of ¹²⁴I-AT-01 and the year is the same as the year of the most-recent date of administration of ¹²⁴I-AT-01, and 2) the end date is on or after the most-recent date of administration of ¹²⁴I-AT-01 or the end date is completely missing, in which case the start day and month will be set to that of the most-recent date of administration of ¹²⁴I-AT-01.
- For a missing end day where the month and year are present, the end day will be set to the last day of the month, unless the month and year are the same as the month and year of the last contact date for the subject, in which case the end day will be set to that of the subject's last contact date.
- For a missing end day and month where the year is present, the end day and month will be set to the subject's last contact date, unless the year of the subject's last contact date is

Page 21 of 38

greater than the end year, in which case the end day and month will be set to December $31^{\rm st}$.

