9.6 Vital Signs

Baseline and all post-baseline visit values and change from baseline to post-baseline values in systolic blood pressure, diastolic blood pressure, heart rate, weight, and body mass index (BMI) will be summarized for the Safety Set using descriptive statistics, as described in Section 4. Height at baseline will be summarized using descriptive statistics, as described in Section 4, and will be used in the calculation of BMI at post-baseline visits.

Vital sign results by visit will be presented in a data listing for subjects in the Safety Set.

Vital signs with clinically significant changes will be summarized and listed as 'flagged' based on the Sponsor's internal guidelines based on Appendix 14.3.

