14.3 Clinically Significant Change in Laboratory Values and Vital Signs

Category	Measurement	Criteria for Clinically Significant Change
Laboratory	Hematocrit (%)	Decrease > 20% and < LLN
_		<pre>Increase > 20% and > ULN</pre>
Laboratory	Hemoglobin (g/dL)	Decrease > 20% and < LLN
_		<pre>Increase > 20% and > ULN</pre>
Laboratory	Leukocytes (x109/L)	Decrease > 20% and < LLN
		<pre>Increase > 50% and > ULN</pre>
Laboratory	Lymphocyte count $(x10^9/L)$	Decrease > 20% and < LLN
		<pre>Increase > 50% and > ULN</pre>
Laboratory	Neutrophils $(x10^9/L)$	Decrease > 20% and < LLN
		Increase > 50% and > ULN
Laboratory	Platelets (x10 ⁹ /L)	Decrease > 20% and < LLN
		Increase > 50% and > ULN
Laboratory	Glucose (mmol/L)	Value < 2.775 mmol/L
		Increase > 50% and > ULN
Laboratory	Bilirubin (umol/L)	Increase > 50% and > ULN
Laboratory	Alkaline phosphatase (IU/L)	Increase > 50% and > ULN
Laboratory	Aspartate Aminotransferase (IU/L)	Increase > 100% and > ULN
Laboratory	Alanine Aminotransferase (IU/L)	<pre>Increase > 100% and > ULN</pre>
Laboratory	Potassium (mmol/L)	Absolute decrease $>$ 0.8 mmol/L and $<$
		LLN
		Absolute increase > 0.8 mmol/L and >
		ULN
Laboratory	Sodium (mmol/L)	Absolute decrease > 0.8 mmol/L and <
		LLN
		Absolute increase > 0.8 mmol/L and >
		ULN
Vital Signs	Systolic Blood Pressure (mmHg)	Decrease > 20 mmHg and SBP < 90 mmHg
Vital Signs	Diastolic Blood Pressure (mmHg)	Increase > 10 mmHg and DBP < 50 mmHg

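### The acute vital-sign change at the second administration is not summarised: change is planned only from the value before the first dose, and the reference for the vital-sign flags is not stated

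*SAP*

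**What the plan says.** **Collection.** The Protocol 1.3 schedule marks heart rate and blood pressure before and after dosing at both Day 1 and Visit 2, with nothing at Screening. Footnote d gives the timing: "Blood pressure and heart rate will be measured within an hour prior to dosing and 5-10 minutes after administration of" the agent. Protocol 4.2.3 says the two doses "will be separated by at least 6 weeks", and the Visit 2 window runs to Week 8.

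**Baseline.** Three statements bear on it:
- Protocol 9.5.4, for vital signs: "Baseline is defined as the last vital signs obtained prior to the initiation of study drug".
- SAP section 4, as a default that other sections may override: "the baseline value for all measures is the last non-missing value prior to the first dose".
- SAP 9.1, for all safety endpoints: "the last non-missing value before administration of" the agent, without saying whether the first or each administration is meant.

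**Analysis.** SAP 9.6 summarises "Baseline and all post-baseline visit values and change from baseline to post-baseline values in systolic blood pressure, diastolic blood pressure, heart rate", weight and BMI. No section plans a change measured from the Visit 2 pre-dose reading.

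**Flags.** SAP Appendix 14.3 flags systolic pressure on "Decrease > 20 mmHg and SBP < 90 mmHg", without naming the value from which the decrease is taken. Its diastolic row pairs a rise of more than 10 mmHg with a value below 50 mmHg. There is no heart-rate row.

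**The concern.** A reading shortly before and another shortly after each dose is a layout for detecting acute effects. On Day 1 the planned analysis uses it that way, because baseline is the same-visit pre-dose reading. At Visit 2 it does not. The post-dose reading is compared with a value taken 6-8 weeks earlier, and the pre-dose reading becomes one more post-baseline value.

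The secondary objective concerns safety under repeated dosing, and change in vital signs is one of its endpoints. Protocol Table 1 lists infusion reactions and immunogenicity as risks, and Protocol 7.1.1.1 names hypotension among the symptoms of a reaction. SAP 9.4.1 already summarises adverse events on the day of dosing for each dosing visit, but the blood pressure data have no matching per-dose summary. At stake are the precision of the estimated acute change at the second dose and whether the systolic flag identifies the right subjects.

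**Working it through.** The plan gives no SD, correlation or precision target for vital signs, so there is no stated figure to reproduce. Let D = Day 1 pre-dose, V = Visit 2 pre-dose and P = Visit 2 post-dose.

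**1. What change from Day 1 contains.** P - D = (V - D) + (P - V). The first term is drift between visits and the second is the acute change. If the tables keep pre-dose and post-dose readings apart, the mean acute change can be recovered in subjects with both values, as mean(P - D) - mean(V - D). Its SD, its range and the number flagged cannot be recovered from those summaries.

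**2. Spread of the two changes.** With a common SD s and correlation r, SD(change) = s × √(2(1 - r)). Assumptions: s = 15 mmHg, r across visits 0.4-0.7, r within a visit 0.7-0.9. The 95% half-width is t(0.975, 19)/√20 times the SD, at n = 20, the planned sample size.

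| Reference | r | SD of change (mmHg) | 95% half-width (mmHg) |
|---|---|---|---|
| Day 1 pre-dose | 0.4 | 15 × √1.2 = 16.4 | 7.7 |
| Day 1 pre-dose | 0.7 | 15 × √0.6 = 11.6 | 5.4 |
| Visit 2 pre-dose | 0.7 | 15 × √0.6 = 11.6 | 5.4 |
| Visit 2 pre-dose | 0.9 | 15 × √0.2 = 6.7 | 3.1 |

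The SD ratio runs from 1.0 (both correlations 0.7) to 2.45 (0.4 against 0.9).

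**3. Systolic flag, exact algebra.** Against Visit 2 pre-dose, a flag needs V - P > 20 and P < 90. The same event is missed against Day 1 when D - P ≤ 20, so D ≤ P + 20 < 110. A miss therefore requires Day 1 SBP below 110 mmHg.

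| D | V | P | Change from Day 1 | Flag | Change from Visit 2 pre-dose | Flag |
|---|---|---|---|---|---|---|
| 105 | 118 | 88 | -17 | no | -30 | yes |
| 125 | 100 | 88 | -37 | yes | -12 | no |

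The Day 1 reference can miss an acute fall, and it can flag drift as if it were acute.

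**4. How often the two references disagree.** This comes from a simulation of 1,000,000 subjects per setting. Assumptions: s = 15, mean SBP 110-120, correlation across visits 0.5 or 0.7, within-visit correlation 0.85.
- With an assumed true acute fall of 30 mmHg, about 10-16% of events flagged within the visit are missed against Day 1. About 5-7% of those flagged against Day 1 are not flagged within the visit.
- With no acute fall, 0.7-3.4% of subjects are flagged against Day 1 and 0.07-0.21% within the visit. About 93-96% of the Day 1 flags are not within-visit flags.

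**5. Diastolic row.** A rise of more than 10 mmHg that ends below 50 mmHg needs a reference below 40 mmHg. A fall cannot meet a condition that requires a rise, so changing the reference does not help this row.

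**The case against.** **The baseline is not beyond doubt.** SAP section 4 is only a default, SAP 9.1 drops the word that ties baseline to the first dose, and SAP section 2 gives the SAP precedence over the protocol. Appendix 14.3 names no reference at all. A reader might infer that the flags are definitely computed from Day 1. The documents do not say so; it follows from SAP section 4 and Protocol 9.5.4. This stands as a limit on certainty, but SAP 9.1 does not set a per-administration baseline either, so the within-visit change remains unplanned.

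**The SAP carries out the protocol's endpoint.** The endpoint is change from baseline, in a descriptive study with no hypothesis. That is correct. The gap is a missing addition, not a departure from anything prespecified.

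**Second-dose reactions are covered elsewhere.** SAP 9.4.1 to 9.4.3 summarise events on dosing days, events by visit period and hypersensitivity events. Vital-sign abnormalities judged clinically significant count as adverse events under Protocol 10.3.1, and all vital signs are listed. A reader might infer that an acute fall at the second dose would go unseen. It would not: a fall from 118 to 88 appears in the listing. What is lost is a systematic summary.

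**The table layout is unknown.** SAP 9.6 and Table 8-1 work by visit without separating pre-dose from post-dose, and table specifications are in separate documents. Whether even the mean acute change can be recovered cannot be settled from these texts.

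**The size depends on the inputs.** A reader might infer that the noise doubles. With a within-session SD w and a visit-to-visit SD b, the ratio is √(1 + b²/w²). It is 1.9-2.0 for (w, b) = (5, 8), (6, 10) and (7, 12), where b is 1.6-1.7 times w. Other plausible inputs give 1.0, which is no gain.

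**Conclusion.** The point holds as a low-cost improvement to the safety analysis. Paired readings exist at both doses, but at the second dose their within-subject difference is not summarised, and the reference for the flags is unstated. The exact results are the decomposition, the 110 mmHg bound on missed systolic flags and the two worked cases. The SD ratio of 1.0 to about 2.5 and the 10-16% of missed flags rest on assumed SDs, correlations and means, and the latter also on an assumed 30 mmHg fall.

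It might be inferred that the Day 1 reference should be replaced. The documents do not support that. Change from baseline is the protocol's endpoint, and a purely within-visit flag would drop the 125, 100, 88 case even though SBP ends below 90.

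**What to change.** - In SAP 9.6, keep the protocol-defined change from baseline for all post-baseline values.
- Add the same-visit change from pre-dose to post-dose in SBP, DBP and heart rate at each dosing visit, and state that pre-dose and post-dose readings are tabulated separately.
- Clarify in SAP 9.1 which administration defines baseline for vital signs.
- In Appendix 14.3, name the reference for the vital-sign flags and report them against both Day 1 pre-dose and same-visit pre-dose, as an addition and not a replacement.
- Reconcile the diastolic row separately, since its two conditions cannot identify a fall under either reference.

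The cost is one derived variable, one table block and a second flag count. No new data are needed.

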10 PHARMACOKINETIC EVALUATION

Not applicable.

11 INTERIM ANALYSES AND DATA MONITORING

The data will be continuously monitored for safety throughout the study. No interim analysis is planned.

Page 27 of 38

12 CHANGES TO THE ANALYSES PLANNED IN THE PROTOCOL

[figure not shown]
Not applicable.

14 APPENDIX

14.1 Study Flow Chart

Abbreviations: CT = computerized tomography; IV = intravenous; PET = positron emission tomography; SoA = schedule of activities.

- a. Begin oral KI for 3 days, beginning >30 minutes and <24 hr prior to dosing.
- b. 124I-AT-01 will be administered by IV infusion over 2-5 minutes (subjects enrolled under protocol Version 1.1) or slow IV bolus at 1 mL/5 seconds (subjects enrolled under protocol Version 2.0). For all subjects, 124I-AT-01 will be administered by the same route (IV infusion over 2-5 minutes or slow IV bolus at 1 mL/5 seconds) at the Week 6 visit as on the Day 1 visit.
- c. Subjects will be discontinued if amyloid deposits are not identified in the Day 1 PET/CT scan in at least one of the following organs: heart, liver, spleen or kidney.
- d. Record concomitant medications and conduct biomarker/safety assessments per SoA.
- e. Safety follow-ups will be done via telephone call for all subjects.

